PROPOSED STUDY TITLE

The Magnitude and Duration of the Central Nervous System Effects following Intravenous Infusion of Diphenhydramine using Pharmacokinetic and Pharmacodynamic Modeling

PRINCIPAL INVESTIGATOR

[name]

NCT NUMBER

NCT05219604

DOCUMENT DATE

2022-FEB-09

SECTION 1.0: STUDY RATIONALE AND SIGNIFICANCE

This study seeks to explore the magnitude and duration of central nervous system (CNS) effects after intravenous (IV) infusion of diphenhydramine. IV diphenhydramine is an antihistamine commonly used in clinical practice as prophylaxis for infusion-related reactions of monoclonal antibodies. Differences in CNS effects between adults aged 35 to 50 and elderly aged 65+ will be explored. This study aims to construct a pharmacokinetic/pharmacodynamic (PK/PD) model describing the magnitude and time course of CNS effects when variables such as dose, rate of infusion, etc. are adjusted. To the knowledge of the investigators, there are no other studies exploring the CNS effects of diphenhydramine with such a wide variety of cognitive tests and as in-depth PK/PD analysis as the present study.

SECTION 2.0: PURPOSE

Objectives:

- To assess the magnitude and duration of CNS impairment produced by intravenous doses of diphenhydramine 50 mg as measured using objective neuropsychometric endpoints.
- To construct a PK/PD model statistically fitted to the individual serum concentrations and CNS impairment data to produce estimates of PK endpoints including area under the curve (AUC), half-life and total clearance as well as PD endpoints including E_{max} (the maximal effect of a drug) and EC_{50} (blood concentrations for 50% of maximum effect).

The PK/PD model will be used to explore the effects on estimates of maximal effect and time course of CNS effect when variables such as dose, rate of infusion, etc. are adjusted.

SECTION 3.0: BACKGROUND

In recent years, the introduction of monoclonal antibodies has significantly increased the number of chronic conditions treated in infusion suites. The reported overall incidence of hypersensitivity reactions to some monoclonal antibodies can be significant. For example, the overall incidence of hypersensitivity reactions to rituximab is reported to be as high as 77% with the first infusion. Fortunately, prophylactic pre-infusion medications can reduce this to less than 10%.¹

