Common medications used alone or in combination with corticosteroids are H1 antihistamines. Until recently this was limited to intravenous diphenhydramine. While intravenous diphenhydramine is effective, it carries with it significant adverse effects. Diphenhydramine readily crosses the blood brain barrier producing both H1 receptor-mediated and cholinergic receptor-mediated effects in the CNS. These CNS effects become more frequent and severe in older patients.

A recently published work found that diphenhydramine was effective in relieving urticarial symptoms but produced subjective "sedation".² Sedation is a depressed state of CNS activity, generally considered a decrease in alertness. However, the effects of diphenhydramine go beyond sedation. There is sufficient published data to suggest that diphenhydramine can have negative effects on several specific domains of cognition including reaction time, recognition and recall, working memory processing speed and ability to perform divided attention tasks. These are many of the same domains of cognition involved in skills related to driving an automobile, etc.³⁻⁷

We propose this study to specifically explore the effects of intravenous diphenhydramine on specific domains of cognition. We propose a formal pharmacokinetic/pharmacodynamic (PK/PD) analysis so that models can be developed that allow estimates of these effects when variables such as dose are varied.

SECTION 4.0: OUTCOME MEASURES

The primary outcome will be the difference in the results of the battery of cognitive function tests (Appendix A) after diphenhydramine administration compared to baseline.

The secondary outcomes will be:

1. The difference in the results of the battery of cognitive function tests in elderly subjects (Group B) vs. adult subjects (Group A)
2. The difference in diphenhydramine area under the curve (AUC) in elderly subjects (Group B) vs. adult subjects (Group A)
3. The difference in the results of the battery of cognitive function tests (Appendix A) after diphenhydramine administration compared to baseline in elderly subjects (Group B) vs. adult subjects (Group A)

SECTION 5.0: INCLUSION CRITERIA

The following are required for inclusion in this study:

- 1) Medically-stable volunteers of either gender between 35 and 50 years old (Group A) or over the age of 65 (Group B)
- 2) No medication changes anticipated for the duration of the study except as defined in section 9.4

SECTION 6.0: EXCLUSION CRITERIA

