^aWomen of child-bearing potential only.

At the screening visit, following provision of informed consent, subjects will provide information regarding their demographics, medical history, concomitant medications and medications taken in the last 4 weeks. Subjects will have their vitals/height/weight measured and undergo a physical exam,

routine clinical blood work (comprehensive metabolic panel and complete blood count), urine toxicology screening, alcohol breath test, and a pregnancy test (women of child-bearing potential as defined in section 9.3).

Subjects meeting all inclusion and exclusion criteria will arrive at the study center for study visit 1 (V1).

During V1, practice cognitive function testing will be conducted to assure each subject has overlearned the test. This is accomplished by having subjects perform each test three times at V1. Prior to cognitive testing, subjects will undergo a urine toxicology screening and alcohol breath test.

Subjects will then return within 7 to 14 days after V1 for study visit 2 (V2). V2 is a treatment day. Subjects will have their vitals and weight measured and will undergo urine toxicology screening, alcohol breath test, and a pregnancy test if indicated. Subjects will then receive treatment with IV diphenhydramine 50 mg at V2. Blood will be drawn for PK samples and cognitive testing will be completed by subjects at predetermined intervals throughout V2. At the end of V2, subjects will have completed the study.

Section 7.2: Study Drug

The study drug will be intravenous diphenhydramine, which will be purchased commercially. Diphenhydramine will be maintained by the study staff and will be administered as per Dent Policy & Procedure INF-024 for intravenous infusion of diphenhydramine (Appendix B), with the exception that diphenhydramine (50 mg) will be administered intravenously by diluting with 5 mL of sterile normal saline and administering as a single bolus injection over 5 minutes.

Section 7.3: Psychometric Testing Study Schedule/Design (Study Visit 2)

Start of Psychometric Testing Time (min from end of administration)	Group A	Group B
0, 30, 210, 450	Subjects 1 – 8	Subjects 1 – 8
0, 60, 240, 480	Subjects 9 – 16	Subjects 9 – 16

Time 0 for conducting psychometric testing will be completed 0 – 60 minutes prior to start of intravenous push. Remaining times represent when the subject will begin psychometric testing. All psychometric tests will begin in a window of +/- 10 minutes.

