The domains of cognitive function that will be measured will be reaction time, movement time, sustained attention, response latency, working memory, visual memory, short-term memory, and new learning. These domains of cognition will be measured before and serially after study drug administration as outlined in the protocol. The specific neuropsychometric tests that subjects will complete are Reaction Time, Rapid Visual Information Processing, Paired Associates Learning, Spatial Working Memory, and Digit Span (Appendix A). These tests have been developed for use in clinical trials by Cambridge Cognition Inc. to assess cognition as a drug safety measure. They have been shown to be sensitive to cognitive decline by pharmacological interventions, confirming their suitability for use in clinical trials to characterize negative effects on various domains of cognitive function.⁸ A Visual Analog Scale will also be used to assess sedation (Appendix A).

SECTION 9.0: ENROLLMENT AND CRITERIA FOR SUBJECT SELECTION

The study will consist of 32 healthy volunteers of any race or ethnicity. Sixteen subjects will be between the ages of 35 and 50 (Group A) and 16 subjects will be aged 65+ (Group B).

Section 9.1: Sample Size Calculation

The expected magnitude of the effect size for impairment and drowsiness is based on our previous work.(7) Taking into consideration the number of subjects that can be reasonably expected to complete the battery of psychometric exams, 32 subjects can be sampled at each of the given time points. Power was calculated using the pwr package in R (version 4.0.2). Using previously published information on cognitive effects of diphenhydramine, this design will result in a power > 0.8 to detect impairing effects of diphenhydramine, and > 0.9 to detect drowsiness effects from diphenhydramine.(7) For impairment, power was calculated at the type I error level of alpha = 0.05 for four sample groups (0, 30-60, 210-240, and 450-480 min) each with 32 subjects/samples and the previously established effect z-score of 0.45. The exact same procedure was used to calculate the power to observe changes in drowsiness scores, but using the previously observed effect z-score of 0.82.

Section 9.2: Females of Childbearing Potential

Females are considered to be of childbearing potential unless they meet one of the following criteria as documented by the investigator:

1. Post-menopausal for at least 1 year
2. Hysterectomy, bilateral oophorectomy, or salpingectomy

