
The PD endpoints, cognitive test result differences between Groups A and B and between baseline and post-diphenhydramine time points, will be assessed via one-way ANOVA with contrast. The PK endpoint will be assessed via one-way ANOVA with contrast of noncompartmental PK analysis. Patient AUCs will be numerically calculated based on patient-specific parameter estimates (i.e, the empiric Bayesian estimates) and compared between Groups A and B.

Section 10.2: Pharmacokinetic/Pharmacodynamic Modeling Strategy

The population PK modeling approach will be implemented using S-ADAPTM. In order to utilize available information in the literature, priors will be obtained for key PK parameters for diphenhydramine in order to leverage a maximum *a posteriori* estimation method. Previous PK studies will be used to supply prior information of the anticipated PK parameters expected from this study. A full step-wise covariate analysis will be done using log-ratio testing with a pre-defined significance level of alpha < 0.05 for forward selection and alpha < 0.01 for backward elimination. Concentrations below the limit of quantification will be handled using the Beal M3 method.

PK data from both Group A (subjects aged 35-50 years) and Group B (subjects aged ≥ 65 years) will be analyzed simultaneously. Patient age will be explored as a possible covariate on the disposition of diphenhydramine.

Intravenous data generated from this study and absorption data following intramuscular administration from literature data will be used to perform model estimates for intramuscular administration.

Continuous PD biomarkers (cognitive test results) will be handled accordingly, which will entail estimation of maximum effect (Emax) and corresponding blood concentrations for 50% of maximum effect (EC50). Categorical PD biomarkers (cognitive test results) will be handled using a hidden Markov method. This method will provide the probability of a patient being at a certain level given the concentration of the drug in the body. This approach has been used extensively to jointly model PK/PD for psychoactive substances.

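### Secondary outcome 1 compares the age groups with no baseline or time point, and the one-way ANOVA in Section 10.1 gives no valid contrast for the age difference in drug effect (outcome 3)

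*Combined protocol and SAP*

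**What the plan says.** Section 1.0 states the age question in terms of drug effect: "Differences in CNS effects between adults aged 35 to 50 and elderly aged 65+ will be explored". Section 4.0 then lists two Group B vs Group A comparisons of the cognitive battery.

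- Secondary outcome 1: "The difference in the results of the battery of cognitive function tests in elderly subjects (Group B) vs. adult subjects (Group A"). It gives no baseline reference, no time point and no stated purpose.
- Secondary outcome 3 is the same comparison, but of results "after diphenhydramine administration compared to baseline in elderly subjects (Group B) vs. adult subjects (Group A").

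The primary outcome is also a change from baseline: "The primary outcome will be the difference in the results of the battery of cognitive function tests (Appendix A) after diphenhydramine administration compared to baseline". Section 7.3 supplies that baseline on the treatment day: "Time 0 for conducting psychometric testing will be completed 0 – 60 minutes prior to start of intravenous push".

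For analysis, Section 10.1 classes these comparisons as PD endpoints and gives the method in one sentence: "cognitive test result differences between Groups A and B and between baseline and post-diphenhydramine time points, will be assessed via one-way ANOVA with contrast". It does not say which contrast serves which outcome. It names no contrast of change between groups and does not mention that each subject contributes four sets of scores. Section 9.0 sets the group sizes: "Sixteen subjects will be between the ages of 35 and 50 (Group A) and 16 subjects will be aged 65+ (Group B").

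**The concern.** Groups A and B are defined by age and not randomised, and the design has no placebo session. Reaction time, attention and memory scores may differ between people aged 35 to 50 and people over 65 before any drug is given. Only the pre-dose test at study visit 2 can remove that difference on the treatment day, and outcome 1 does not use it. Outcome 1 cannot simply be shorthand for change, because outcome 3 repeats the comparison and adds the baseline reference.

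The unadjusted comparison has a named test in Section 10.1, while the informative one does not. If the four scores per subject enter a one-way ANOVA as independent values, the error term is wrong for both: too small for A vs B, too large for the difference in change. The trial could then report a significant outcome 1 beside a null outcome 3, with no rule for which one answers the age question. Section 3.0 already states that CNS effects are more frequent and severe in older patients, so poorer scores in Group B could easily be taken as confirmation.

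**Working it through.** **1. The plan's own figure.** Section 9.1 claims power above 0.8 (effect 0.45) and above 0.9 (effect 0.82) at alpha 0.05, with four time groups of 32. Entering the effects as Cohen's f in a balanced one-way ANOVA, the noncentrality is 4 × 32 × f²:

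- f = 0.45: 128 × 0.2025 = 25.9, power 0.993.
- f = 0.82: 128 × 0.6724 = 86.1, power above 0.999.

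Both bounds are met on that reading. The calculation concerns change over time in all 32 subjects and covers no A vs B comparison. It also treats the time points as separate samples: "For impairment, power was calculated at the type I error level of alpha = 0.05 for four sample groups".

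**2. Inputs for the A vs B check.** From the documents: 16 per group, one pre-dose and three post-dose tests, alpha 0.05 (taken as two-sided). Assumed, because the documents give neither: a pre-existing age gap of 0.5 or 1.0 SD and a within-subject correlation r of 0.5 to 0.7, equal for all pairs of tests. The drug effect is set equal in both groups. Scores are in SD units.

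**3. Unadjusted comparison of subjects' post-dose means.** The variance of a mean of three tests is (1 + 2r)/3, so the SD is 0.816 at r = 0.5 and 0.894 at r = 0.7. The noncentrality of the two-sample t-test (30 df) is (gap/SD) × √(16/2).

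| Age gap | r = 0.5 | r = 0.7 |
|---|---|---|
| 0.5 SD | 0.612 × 2.828 = 1.73, rejects 39% | 0.559 × 2.828 = 1.58, rejects 33% |
| 1.0 SD | 1.225 × 2.828 = 3.46, rejects 92% | 1.118 × 2.828 = 3.16, rejects 86% |

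For one post-dose test (SD 1) the rates are 28% and 78%. The gap cancels in change from baseline. Simulated rejection on change scores is 5% at every gap.

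**4. A vs B when repeated scores are treated as independent, no age gap.** With three post-dose scores per subject, the true variance of the group difference is 1 + 2r times the assumed one: 2.0 or 2.4. The nominal cut-off of 1.96 is then really 1.96/√2.0 = 1.39 or 1.96/√2.4 = 1.27, and the rejection rates are about 17% and 21%. Simulation gives 16% and 21%. Averaging over all four tests gives 21% at r = 0.5.

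**5. The outcome 3 contrast in the same ANOVA, no difference in drug effect.** The true variance of a change contrast is 1 − r times the assumed one: 0.5 or 0.3. The real cut-off is 1.96/√0.5 = 2.77 or 1.96/√0.3 = 3.58, giving rejection of 0.6% and 0.03%. Simulation with the error variance estimated gives about 0.7% and 0.1%.

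**6. What that costs.** Suppose the drug effect differs by 0.8 SD between groups at all three post-dose tests (assumed). At r = 0.5 the change (mean of three minus baseline) has variance (4/3) × 0.5 = 0.667, so the standard error of B minus A is √(0.667 × 2/16) = 0.289 and the effect is 0.8/0.289 = 2.77 standard errors. Against the real cut-off of 2.77, power is about 50%. A t-test on change scores (cut-off 2.04) has about 76%. At r = 0.7 the corresponding figures are about 50% and 93%.

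**The case against.** The strongest reply is that the plan already contains the remedy. Outcome 3 is the baseline-referenced age comparison, the primary outcome is a change from baseline, and the pre-dose test is scheduled. Listing outcomes 1 and 3 separately suggests that outcome 1 is about score level, which is a legitimate quantity in a study that wants to simulate test performance. Age differences are only to be explored, and Section 2.0 lists no age objective. This stands in part. It is why outcome 1 need not be deleted, and why the point concerns labelling and method and not a missing comparison.

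A reader might go further and infer that ordinary age differences will be read as a greater drug effect in the elderly. The documents do not support that. No passage assigns this meaning to outcome 1, none ranks the secondary outcomes, and outcome 1 names no time point, so a post-dose comparison is only one reading of it. What remains is that Section 10.1 places the group difference among the PD endpoints and nothing labels it descriptive, so the misreading is open.

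It can also be said that Section 10.1 does not state that scores are treated as independent, and that a one-way ANOVA on one change score per subject would be valid. That is true. But the section names no such summary, and Section 9.1 handles the four time points as four sample groups.

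Finally, the rates in step 3 are the power to detect a gap that was put in. They are errors only if the result is attributed to the drug. The inflation in step 4 is a separate fault and should not be added to them.

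**Conclusion.** The concern holds in a limited form. As worded, outcome 1 cannot separate age from drug effect. Outcome 3 can, but the stated method does not specify it, and a one-way ANOVA that ignores the repeated measures is invalid for both comparisons. Under equal drug effects, the unadjusted comparison of post-dose means rejects in about 33 to 39% of trials at a 0.5 SD gap and 86 to 92% at 1.0 SD, against 5% for change. The independence ANOVA rejects A vs B in about 17 to 21% with no gap at all, and the outcome 3 contrast in only about 0.1 to 0.7%.

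The size depends on the assumed gap and correlation. The 5% for change also assumes an additive drug effect, no floor or ceiling in the scores, and no other age-dependent trend over the test day. The direction of each error does not depend on the exact values, provided scores within a subject are positively correlated. Because the age comparison is secondary and exploratory, this should be corrected but does not threaten the primary outcome.

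**What to change.** In Section 10.1, replace the one-way ANOVA for these comparisons with a repeated-measures model for each test, with group, time and group-by-time as fixed effects and subject as a random effect. Define outcome 3 as the group-by-time contrast of change from the visit 2 pre-dose test, and state that inference on an age difference in drug effect rests on this contrast.

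In Section 4.0, give outcome 1 a time point (for example the visit 2 baseline) and label it a descriptive comparison of score level, not a drug effect. It does not have to be deleted.

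The cost is a few sentences in two sections. All the data are already scheduled. The downside is one fewer inferential secondary outcome.

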The following will be considered exclusionary for participation in this study:

- 1) Insulin-dependent diabetes
- 2) Psychiatric or neurologic disease affecting cognition in a way that may interfere with study outcomes in the opinion of the investigator
- 3) Unstable Coronary Artery Disease (active angina, MI within 6 months, stent placement within 6 months, cardiac surgery within 6 months)
- 4) Estimated CrCl < 30 mL/min using the Cockroft-Gault equation based on ideal body weight or total body weight
- 5) Any malignancy actively being treated or not in remission
- 6) Currently taking any CNS stimulant or depressant medications that may interfere with study outcomes in the opinion of the investigator unless using as defined in section 9.4
- 7) Positive toxicology test for marijuana at screening visit or visit 2 or using marijuana not as defined in section 9.4
- 8) Active or recent history of a substance use disorder within one year
- 9) Any medical condition that in the opinion of the investigator would disqualify the subject from participation in the study
- 10) Female subjects who are pregnant, planning to become pregnant, or breastfeeding on any study day
- 11) Female subjects of childbearing potential unwilling to use acceptable method of contraception during the study as defined in section 9.3
- 12) Contraindication, known allergy, or suspected intolerance to study medication
- 13) Receipt of an antihistamine (details in section 9.4) within 5 half-lives prior to the start of study visit 1 or study visit 2, as determined by the investigator

14) Positive toxicology test for a drug that is inconsistent with permitted medication use (defined in section 9.4) as interpreted by the investigator
 15) Participation in any other investigational drug study during the study or within 4 weeks prior to screening

SECTION 7.0: METHODS

Section 7.1: Overview

Table 1. Schedule of study assessments.

Assessment	Screening Visit (V0) (Day 0)	Study Visit 1 (V1) (Day 7 +/- 3)	Study Visit 2 (V2) (Day 14 +/- 7)
Demographics	X		
Medical history	X		
Prior/concomitant medications	X		X
Review health and any changes in health	X	X	X
Vital signs	X		X
Weight	X		X
Height	X		
CBC and CMP	X		
Diphenhydramine PK			X
Urine pregnancy test ^a	X		X
Urine toxicology test	X	X	X
Alcohol breath test	X	X	X
Physical exam	X		
Cognitive tests		X	X
Infusion with diphenhydramine			X

CBC = complete blood count, CMP = comprehensive metabolic panel, PK = pharmacokinetics

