Measurements will be taken pre-treatment, just after infusion (30-60 min post-infusion), half-way (210-240 min post-infusion), and at the end (450-480 min post-infusion) of the experiment. This design was selected to generate a robust set of richly collected psychometric testing data that can be analyzed over the full-time course of the experiment. In addition, the population PK/PD analysis method to be implemented (see below) will permit a “sharing” of information between subjects. This strategy will permit robust sampling of the psychological effects of each drug after a single dose, and relate these effects to the concentration of diphenhydramine.

Section 7.4: Pharmacokinetic Sampling Schedule/Design (Study Day 2)

All subjects will have PK samples drawn at the following time points from end of study drug administration:

PK Sample Time (min from end of administration)	Acceptable Range (min)
15	+/- 5
30	+/- 5
60	+/- 5
90	+/- 5
120	+/- 5
180	+/- 10
210	+/- 10
360	+/- 10
420	+/- 10
480	+/- 10

Additionally, a sample will be drawn at time 0 at 0-60 minutes prior to start of drug administration.

At time points where both PK samples are taken and psychometric testing is completed, the PK sample will be taken prior to the start of psychometric testing.

Given the limited population of PK data in the literature for diphenhydramine, a rich sampling scheme will be implemented for each subject. The frequent samples after the end of administration at 15, 30, and 60 min will capture the distributional phase of diphenhydramine. Furthermore, by richly sampling all 32 subjects, this will allow for adequate description of PK fixed effects (clearance, volume of distribution, etc.) and the corresponding inter-individual variabilities on each of those terms.

Section 7.5: Adverse Events (AEs)

Subjects will be under continuous observation at the study site. Both medical and nursing staff will be at the study site for the entire study day. Any subject reporting AEs during the study day will be medically evaluated as appropriate. All AEs and treatments will be recorded in the subject's study file. Serious adverse effects will be reported to the IRB according to IRB reporting policy. Subjects will be given direct phone numbers to report any adverse event after discharge from the study site.

SECTION 8.0: ASSESSMENTS

Section 8.1: Battery of Cognitive Function Tests

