A total of 13 tubes (about 4 tablespoons) of blood will be drawn over the course of the study. As a reference point, when donating blood to an organization such as the Red Cross, approximately 16 ounces or 32 tablespoons of blood are taken. The blood draws may be painful and cause redness, bruising, or infection at the site of needle entry. Sometimes, people experience dizziness and faint or feel nauseous. Experienced medical personnel will be responsible for blood draws to minimize these risks.

Participants will receive diphenhydramine on study visit 2. Diphenhydramine is FDA approved for use and has demonstrated safety. However, diphenhydramine may cause side effects, many of which are more common in the elderly. Possible side effects of diphenhydramine include drowsiness, confusion, lack of concentration, memory impairment, blurry vision, dry mouth, urinary retention, nausea, constipation, agitation, and delirium. Rare but serious side effects of diphenhydramine include allergic reaction and fainting. In addition, the use of diphenhydramine has been linked to accidental injury. Subjects may feel some of the effects of diphenhydramine on the day following the infusion.

Diphenhydramine will be infused intravenously once on study day 2. Intravenous (IV) infusion involves placement of a needle into the vein. For most people, needle sticks for IV injections do not cause any serious problems. Sometimes they may cause bleeding or bruising. They may also cause infections and/or pain at the needle site. Sometimes, people experience dizziness and faint or feel nauseous. Placing the IV line will be done with sterile equipment, but germs on the skin may enter through the skin around the IV, causing swelling, redness, and fever. Phlebitis is irritation of a vein. Subjects may feel swelling, pain, and redness around the vein. A blood clot or an air bubble can be delivered into the circulation through an IV and end up blocking a vessel; this is called embolism. There is a low risk of this. Extravasation is accidentally putting the drugs into the surrounding tissue instead of the vein. Experienced medical personnel will be responsible for infusing diphenhydramine to minimize these risks.

Subjects will be asked to perform an alcohol breath test. This involves forcefully blowing air into a breathalyzer device. Subjects may experience some lightheadedness, fatigue, or shortness of breath after this test.

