A urine toxicology test is a test of the urine. The test checks for recent drug use. Subjects will be asked to urinate or “pee” into a small cup. The test involves only normal urination. There is usually no discomfort.

Subjects will be asked to perform cognitive tests on an electronic device during this study. Subjects will also be asked to complete some surveys on paper. Subjects may experience some fatigue, frustration, boredom, or eye strain from these tests.

The investigators will collect subjects' personal information including health-related information for this study. Although there are many safeguards protecting subject information, there is always a risk that the confidentiality of information is breached.

Subjects will be asked to come to the study site for several hours to complete this study. It is estimated that V0 will take around 3 hours, V1 will take around 2 hours, and V2 will take around 9 hours. This may result in financial loss for subjects if they must take time off work to attend study visits.

Subjects will be counseled on the symptoms associated with adverse events so that they may monitor for them. Additionally, subjects will be asked for the presence of any adverse events at every visit specifically including side effects associated with diphenhydramine use.

SECTION 14.0: BENEFITS

Participation in this study will not provide direct benefit to the population. It may, however, provide insight into CNS effects of diphenhydramine which may impact patient care in the future.

SECTION 15.0: COMPENSATION FOR STUDY PARTICIPANTS

For taking part in this research, subjects may be paid up to a total of \$200. Compensation will be broken down as follows:

- \$75 at screening visit, \$25 at study visit 1, \$100 at study visit 2
- Payments will be initiated following the final study visit
- Subjects will not be paid for any visits that they do not complete

SECTION 16.0: ALTERNATIVE TO PARTICIPATION

The alternative to be involved in this study is to not participate.

SECTION 17.0: STUDY START AND END DATES

Section 17.1: Enrollment Start Date

Upon IRB approval via central IRB. IRB review is anticipated within 30 days of Submission.

Section 17.2: Screening and Data Collection

To begin immediately following IRB approval. Data collection is expected to be complete within 6 months of IRB approval.

Section 17.3: Anticipated Manuscript Submission

Within 6 months of completion of data collection.

SECTION 18.0: INFORMED CONSENT PROCESS

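### In the visible protocol text, active adverse-event questioning ends with V2, about 8 to 9 hours after the only dose, so mild next-day events may be under-recorded

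*Combined protocol and SAP*

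**What the plan says.** Section 7.1 describes a screening visit (V0), a practice visit (V1) and a treatment visit (V2). Diphenhydramine is given once, at V2, and the section closes the subject's participation there: "At the end of V2, subjects will have completed the study". Table 1 has no column after V2, and its row "Review health and any changes in health" is marked for V0, V1 and V2 only.

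Section 13 sets out how events are elicited: "subjects will be asked for the presence of any adverse events at every visit specifically including side effects associated with diphenhydramine use". It also says: "Subjects will be counseled on the symptoms associated with adverse events so that they may monitor for them". The same section warns: "Subjects may feel some of the effects of diphenhydramine on the day following the infusion".

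Section 7.5 provides continuous observation on the study day, with medical and nursing staff present throughout, and states that all adverse events and treatments are recorded. On evaluation it says: "Any subject reporting AEs during the study day will be medically evaluated as appropriate". For the time after the subject leaves, it says: "Subjects will be given direct phone numbers to report any adverse event after discharge from the study site".

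**The concern.** The protocol names a period in which subjects may still feel the drug, and its scheduled questioning stops before that period begins. From discharge onward, an event enters the record only if the subject decides to telephone. Mild events are the ones a subject is least likely to call about, so the record may look cleaner for the following day than it should.

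Two features of the study make the next day worth asking about. Half of the sample (16 of 32) is the older group, and Section 13 says that many of the side effects are more common in the elderly. The study also sets out to describe how long CNS effects last. A short next-day symptom record would be useful descriptive context for that aim, although it would not enter any planned analysis.

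At stake are the completeness of the safety description and one scheduled occasion for staff to learn of a problem and respond.

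**Working it through.** No power or sample-size formula bears on this point. The check is a timeline followed by a comparison of the sections.

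**Inputs**
- Push: 5 minutes (Section 7.2).
- Pre-dose PK sample and baseline tests: 0 to 60 minutes before dosing (Sections 7.3 and 7.4).
- Last cognitive battery: starts at 450 or 480 minutes, ±10 (Section 7.3).
- Last PK sample: 480 ± 10 minutes after the end of administration, in all subjects (Section 7.4).
- Length of V2: "V2 will take around 9 hours" (Section 13).

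**Step 1: reproduce the stated visit length.** Pre-dose period + push + last scheduled sample:
- shortest: 0 + 5 + 480 = 485 minutes = 8.1 hours
- longest: 60 + 5 + 480 = 545 minutes = 9.1 hours

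This agrees with the protocol's figure of around 9 hours.

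**Step 2: find when active coverage ends after the dose.**
- From the last PK sample: 470 to 490 minutes = 7.8 to 8.2 hours after the push.
- From the visit length: (540 − 60 − 5) to (540 − 0 − 5) = 475 to 535 minutes = 7.9 to 8.9 hours after the push.

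Questioning can therefore reach to about 8 to 9 hours after the dose, or 8/24 = 33% to 9/24 = 38% of the first 24 hours. The text does not say when within V2 the question is put, so this is the latest it could be.

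**Step 3: count the visits that can elicit a drug-related event.** Questioning is tied to visits. V0 and V1 come before the dose, so 1 of the 3 visits (V2) contains any post-dose time. The visible text shows no scheduled contact after V2.

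**Step 4: compare the two periods.**

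| | During V2 | After discharge |
|---|---|---|
| Who starts the contact | Staff | Subject |
| Means | Continuous observation, questioning specific to diphenhydramine | Symptom counselling, direct telephone numbers |
| Effects anticipated by Section 13 | Yes | Yes, on the following day |

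Only the scheduled, staff-initiated element is missing from the right-hand column.

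**Step 5: trace the consequence.** Section 4.0 lists cognitive test results and AUC as outcomes; adverse events are not among them. Section 10 plans no adverse-event analysis. The cognitive and PK data are all collected within V2. Nothing that happens to next-day reports changes a planned test or model.

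**The case against.** The strongest reply is that post-discharge events are already provided for. Subjects are told what to watch for and given a direct line, and the commitment in Section 7.5 to record all adverse events has no time limit. For one dose of an approved, commercially purchased drug, with a full day of observation and a last cognitive battery at 450 to 480 minutes, an inbound line can be called a reasonable choice. The next-day warning is a single precautionary sentence with no type, frequency or severity attached. No planned analysis would change.

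Most of this stands, and it is why the point is minor. What it does not answer is that the protocol anticipates next-day effects and leaves their recording to the subject's initiative, when asking everyone once would cost little.

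The unseen text also matters. Appendix B (infusion policy) and Appendix C (consent process) are attachments that could not be read, and either may contain a follow-up instruction. The point is therefore limited to what is visible.

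A reader might infer three stronger things that the documents do not support:
- That subjects who call later would go unevaluated. The evaluation sentence in Section 7.5 describes care for events reported on the study day; it does not exclude later callers.
- That lingering confusion or memory impairment would stop subjects from calling. Section 13 lists these as possible side effects but does not say that they are among those that last to the next day.
- That a definite number or share of events will be lost. Any such figure would rest wholly on assumed event and reporting rates, and under some assumptions the loss is nil.

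**Conclusion.** The point holds as a minor, inexpensive improvement. In the visible text, active questioning ends with V2, about 8 to 9 hours after the dose, and the following day is covered only by counselling and calls that the subject starts. Mild next-day events may be under-recorded.

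The effect is confined to the descriptive safety record and to subject follow-up. It leaves the primary outcome, the group comparisons, the PK results and the PK/PD model untouched. Its size in events cannot be stated.

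The conclusion rests on two assumptions: that the unread appendices do not already require a next-day contact, and that some subjects with mild symptoms would mention them if asked but would not telephone unprompted.

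**What to change.** Add one scripted telephone contact by existing staff on the day after V2, for all 32 subjects. The script should go through the side effects listed in Section 13 and ask about falls or injuries, since that section mentions accidental injury without saying when it occurs. Then:
- show the call as a column in Table 1 and describe it in Section 7.5;
- define study completion in Section 7.1 as following the call;
- list next-day events descriptively by age group;
- keep the telephone numbers and the counselling.

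If Appendix B or C already requires a call, carry it into Table 1 and Section 7.5 instead of adding a second one.

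The cost is a short amendment and 32 brief calls, with no extra visit or procedure and no change to sample size or endpoints. Some calls may go unanswered, and the reported event counts may rise because events are being asked about.
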